#### 4.2. Secondary Objective

The secondary objective of this study is to summarize the distribution of improvements in patients' self-reported assessment of postoperative function and quality-of-life from baseline to a maximum of 12 months. Additionally, other pre-operative planning alignment goals (e.g. Knee V-V Alignment; Femoral Joint Line Alignment Angle; Tibial Joint Line Alignment Angle; Tibial Slope Angle) will be compared to the post-operative alignment.

### 5. STUDY DESIGN

This clinical investigation will be conducted as a prospective, non-randomized, multicenter study. Investigators will recruit patients from patients in their practice who require unilateral total knee arthroplasty. Patients will be screened to identify eligible candidates based on the inclusion and exclusion criteria described in Sections 6.1 and 6.2. A total of one hundred fifteen (115) patients will be enrolled in the study across the participating sites. All patients will sign an informed consent form prior to participating in the study. Prior to the investigational procedure, they will complete baseline surveys of function and quality of life and have baseline radiographs. Each patient will undergo robotic-assisted total knee arthroplasty with the TSolution One System. The Investigator will evaluate intra- and postoperative complications. Postoperative radiographs will be used to measure limb alignment using a standardized radiographic evaluation protocol for the IDE Study Arm (Attachment K of the IDE application). Each patient will complete a postoperative Knee Society Score survey and the SF-12 Health Survey to assess functional outcomes and quality-of-life following the investigational procedure.

The clinical study will have two arms: the IDE Study Arm, and the Continued Access Arm. Once enrollment is complete in the IDE Study Arm, subjects will be enrolled into the Continued Access Arm. Up to an additional 50 patients will be enrolled in this arm.

The TSolution One™ Total Knee Arthroplasty Clinical Trial will be conducted in compliance with this protocol, Good Clinical Practice (GCP) guidelines, and applicable US regulatory requirements.

#### 5.1. Primary Effectiveness Endpoint

The primary effectiveness endpoint is alignment of coronal mechanical axis at 3 months defined as achieving varus-valgus alignment less than or equal to  $\pm 3^\circ$  in the frontal plane after TKA compared to the pre-operative plan. A review of 1,376 patients undergoing conventional TKA with manual instrumentation showed a 32% malalignment for mechanical axis greater than 3° (Mason). This

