Outcome Measurements	
Primary Effectiveness Endpoint - The primary effectiveness endpoint is alignment of coronal mechanical axis at 3 months defined as achieving varus-valgus alignment less than <math>\pm 3^\circ</math> in the frontal plane after TKA. A review of 1,376 patients undergoing conventional TKA with manual instrumentation showed a 32% malalignment for mechanical axis greater than <math>3^\circ</math> (Mason). This study is designed to demonstrate that the investigational device is capable of reducing the malalignment rate by 50%, that is, to 16%.
 
Primary Safety Endpoint - The primary safety endpoint is a composite safety endpoint that includes a number of relevant adverse events identified in a literature search, each having an expected incidence <math>\leq 2.7\%</math>. The sum of these relatively rare complications is equal to 7.6%. The percentage of patients with TCAT-assisted implantation using the TSolution One System for TKA experiencing the composite safety event will be compared to 7.6%.
 
Secondary Safety Endpoints
 
 
• Bleeding complications are not rare and will be assessed separately as a secondary safety endpoint based on the incidence of transfusions (allogeneic or autologous).
 
• Complications related to excessive bleeding that require surgical intervention will be assessed and summarized as a subset of the bleeding complications above.
 
• Other secondary safety endpoints include the incidence of the individual adverse events comprising the composite.
 
 
Secondary Effectiveness Endpoints
 
Effectiveness endpoints are considered secondary for this study and are summarized below:
 
 
• Postoperative function will be evaluated by collecting Knee Society Scores at 3, 6, and 12 (if available) months.
 
• Health related quality-of-life will be assessed by collecting Short Form 12 (SF-12) Health Survey scores at 3, 6, and 12 (if available) months.
 
• Post-operative alignment outcomes will be compared to pre-operative alignment goals at 3 months.
 

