#### **THINK Surgical, Inc.**

Proprietary rights of THINK Surgical, Inc. are involved in the subject matter of this material. It is submitted in confidence for a specific purpose and the recipient by accepting this material agrees that it will not be used other than for the express purpose for which it was delivered.

Disclosure to others without written permission from THINK Surgical, Inc. is forbidden.

malalignment for mechanical axis greater than 3° at 3 months to the rate reported in the literature (i.e. 32%) and to demonstrate significant clinical benefit by reducing the number of malaligned patients by at least 50% (i.e. from 32% to ≤16%). The safety objective of this study will be based on the rate of intra-operative and postoperative TKA complications, and will compare this rate to the rate reported in the literature.

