## 5.3. Secondary Endpoints

Bleeding complications have an expected incidence of 36% for unilateral TKA (Bierbaum et al. 1999), and are not rare. These will be assessed separately as a secondary safety endpoint at discharge based on the incidence of transfusions required (autologous or allogenic) as a result of bleeding.

Descriptive safety analyses for the incidence of the individual adverse events comprising the composite will also be performed.

The secondary endpoints also include a comparison of post-operative alignment outcomes other than coronal mechanical axis to the pre-operative alignment goals, and assessment of improvements in Knee Society Scores and SF-12 Health Survey scores.

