#### 15. RADIOGRAPHIC ENDPOINT ASSESSMENT

Radiographic assessment of the efficacy endpoints (i.e. coronal alignment relative to the mechanical axis, and post-operative alignment outcomes) will be performed by protocol-trained radiologists at an independent core imaging lab per the TSolution One IDE Radiographic Evaluation Protocol.

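### The co-primary effectiveness endpoint has two definitions, one measured from the surgical plan and one not, and the 32%/16% benchmark is described only for the mechanical axis

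*Combined protocol and SAP*

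**What the plan says.** **Text that measures from the plan**

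- Section 5.1 sets the limit at 3° or less, "in the frontal plane after TKA compared to the pre-operative plan".
- Section 5.3 is consistent with this. Its secondary endpoint is "a comparison of post-operative alignment outcomes other than coronal mechanical axis to the pre-operative alignment goals", which leaves the coronal axis to the primary endpoint.

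**Text that does not**

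- The Section 1 summary gives the primary endpoint as "alignment of coronal mechanical axis at 3 months defined as achieving varus-valgus alignment less than" 3° either way, with no plan mentioned.
- The same summary lists as secondary: "Post-operative alignment outcomes will be compared to pre-operative alignment goals at 3 months". It makes no exception for the coronal axis.
- Section 4.1 (primary objective) compares the rate of mechanical-axis malalignment beyond 3° with the literature's 32%, again without a plan.
- Section 15 has the core laboratory assess "coronal alignment relative to the mechanical axis, and post-operative alignment outcomes".

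**Text that points both ways**

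- Section 4.2 makes secondary the "other pre-operative planning alignment goals (e.g. Knee V-V Alignment" and further angles. The first word fits Section 5.1; the varus-valgus example fits the summary.

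**The benchmark.** Sections 1, 4.1, 5.1 and 9.2 all describe the 32% as a mechanical axis more than 3° out in conventional surgery. The 0.16 bound is half of it. Section 9.2 assumes a true rate of 0.07 without naming its reference.

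**Status of the endpoint.** Under Section 1's success criterion, both the effectiveness and the safety test must succeed. Yet the summary's secondary list opens with "Effectiveness endpoints are considered secondary for this study and are summarized below".

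**The concern.** The event counted by one of two decisive tests depends on which section is followed. Section 7.1 lets the investigator position the implant in the planning software, and no section requires a neutral plan. A knee planned away from neutral and cut exactly to plan is a success under Section 5.1 but may count as malaligned on the mechanical axis. A knee that misses its plan by more than 3° may still end up close to neutral.

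What can be claimed also changes. Passing under Section 5.1 shows that fewer than 16% of knees miss their own plan by more than 3°. By itself, that does not establish the benefit stated in Section 4.1, a fall in malaligned patients from 32% to 16% or less. With both definitions in the current text, the choice could be made after the alignment results are known.

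The cut-off differs as well. A knee at exactly 3° is aligned under Section 5.1 and under the benchmark's wording, but malaligned under the summary.

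**Working it through.** **1. The plan's own figure.** Inputs from Sections 1 and 9.2: N=103, null rate 0.16, true rate 0.07, one-sided α=0.05, exact binomial test. The pass limit is the largest c with P(X ≤ c | 103, 0.16) ≤ 0.05.

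- P(X ≤ 10) = 0.0476
- P(X ≤ 11) = 0.0856

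So c = 10, and one knee can decide the result. Power = P(X ≤ 10 | 103, 0.07) = 0.894, against 89.3% stated. The claim of power above 80% from N=95 also holds: 0.872 at 95, with a minimum of 0.823 (at 102) over N=95 to 200. The arithmetic is sound; the open question is which event X counts.

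**2. Sensitivity to the rate.** Chance of passing, P(X ≤ 10 | 103, p):

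| True rate p | 0.05 | 0.07 | 0.08 | 0.10 | 0.12 |
|---|---|---|---|---|---|
| Chance of passing | 98.6% | 89.4% | 79.9% | 54.4% | 29.6% |

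Modest differences in rate between the two definitions therefore matter.

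**3. Illustration of the gap.** The documents give no distribution of planned alignment, so everything here is assumed. Execution error (achieved minus planned) is normal with mean 0. The plan's offset from neutral is normal with mean 0 and SD τ, independent of the error.

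*(A) The 7% is measured from plan.* P(|error| > 3) = 0.07 gives σ = 3/1.812 = 1.656°. Measured from neutral, SD = √(1.656² + τ²) and rate = 2[1 − Φ(3/SD)]. For τ = 1.0: SD = √(2.742 + 1) = 1.934, 3/1.934 = 1.551, rate 12.1%.

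| Plan SD τ | Rate from neutral | Chance of passing on that rate | Knees of 103 classed differently |
|---|---|---|---|
| 0 | 7.0% | 89% | 0 |
| 0.25° | 7.3% | 87% | about 2 |
| 0.5° | 8.3% | 77% | about 4 |
| 1.0° | 12.1% | 29% | about 9 |
| 1.5° | 17.9% | 1.5% | about 16 |

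The last column comes from 4 million simulated knees. A constant plan offset instead of a varying one gives similar figures: 0.5° gives 8.3% and a 77% chance of passing; 1° gives 12.1% and 28%.

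*(B) The 7% is measured from neutral.* The neutral-referenced test keeps its 89% power. Measured from plan, SD = √(1.656² − τ²). For τ = 0.5 this is 1.579, a rate of 5.7% and a 97% chance of passing. For τ = 1.0 it is 1.320, a rate of 2.3% and a chance above 99.9%.

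**4. Cut-off.** If films are read to 0.1° (assumed) and σ = 1.656°, the share read as exactly 3.0° is 0.93%, and 0.0093 × 103 is about 1 knee.

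**The case against.** **Only one reference is stated.** Section 5.1 names the plan. The summary and Section 4.1 name nothing, and neutral is an inference from the straight-line axis described in Section 2.1. Sections 5.1 and 5.3 agree with each other, and the revision history for versions 3.0 and 3.1 records a move towards the surgeon's goals in place of neutral. This is good evidence of intent and suggests that the summary was not updated. But a change log does not amend current text. The summary actively places the plan comparison among the secondary endpoints, and Section 15 speaks of alignment relative to the mechanical axis.

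**The 32% may itself be error from target.** Section 2.1 says manufacturers advised restoring the ideal axis and presents this literature, citing the same source, as alignment error despite the surgeon's intentions. If conventional surgeons aimed at neutral, deviation from plan is a comparable kind of quantity. This stands, and it is why no direction of bias is claimed. It is an argument the sponsor could make, but the protocol does not make it.

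**The pass rates rest on assumed spreads.** That is so: they run from no effect to near-certain failure, and under (B) the neutral test loses nothing. They show that the choice can matter, not that it does here. The case for correction rests on the conflicting text.

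**The Radiographic Evaluation Protocol may fix the reference.** It was not supplied. It may fix how the core laboratory measures, but it does not settle which of the protocol's two definitions is tested, or justify 0.16 for it.

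**The minor items are small.** Agreed. The cut-off affects about one knee, and the sentence calling effectiveness secondary is leftover wording with no effect on the analysis.

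**Conclusion.** The concern holds and must be fixed. The current text carries two definitions of a co-primary pass/fail endpoint, differing in reference and in cut-off, and the bound is described only for the mechanical axis. The planned power is correct for a true rate of 0.07, but the protocol does not say from which reference that rate is measured.

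The size of the problem cannot be fixed from the documents because they give no spread of plans. Under the stated assumptions (normal, independent, centred on zero), a plan SD of 0.5° to 1.0° reclassifies about 4 to 9 of 103 knees. With the 7% measured from plan, the chance of passing on the neutral rate falls from 89% to between 77% and 29%. If every plan is neutral, the definitions coincide apart from the cut-off. Whether the plan reference favours the device is not shown.

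**What to change.** State one reference and one cut-off, with malaligned meaning more than 3° to match the benchmark, in the Section 1 summary and in Sections 4.1, 4.2, 5.1, 5.3, 9.2 and 15. The choice of reference is the sponsor's:

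1. **Mechanical axis (neutral) as primary.** Test that rate against 0.16 and report deviation from plan as secondary.
2. **Pre-operative plan as primary.** Justify 0.16 for a plan-referenced rate. Report beside it the neutral-referenced rate from the same 3-month long-leg films against 0.16, and rest the claim of halving 32% on that neutral rate alone.

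In either case, Section 9.2 should say which reference the assumed 7% uses, and the summary's sentence calling effectiveness endpoints secondary should be deleted.

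The cost is wording plus, at most, one further tabulation from films the core laboratory already reads. The sponsor should accept that the neutral-referenced rate may prove less favourable than the plan-referenced one.

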#### THINK Surgical, Inc.

Proprietary rights of THINK Surgical, Inc. are involved in the subject matter of this material. It is submitted in confidence for a specific purpose and the recipient by accepting this material agrees that it will not be used other than for the express purpose for which it was delivered.

Disclosure to others without written permission from THINK Surgical, Inc. is forbidden.

study is designed to demonstrate that the investigational device is capable of reducing the malalignment rate by 50%, i.e. to 16%.

*Note: The primary effectiveness endpoint will be evaluated utilizing only the IDE Study Arm.*

## 5.2. Primary Safety Endpoint

The primary endpoint is a composite endpoint that includes a number of relevant adverse events associated with manual TKA that were defined and published by the Knee Society (Healy et al. 2011), each having an expected incidence  $\leq 2.7\%$  based on a literature search summarized in Table 1. The sum of these relatively rare complications is equal to 7.6%. The percentage of patients with TCAT-assisted implantation experiencing the composite safety event will be compared to 7.6% plus a non-inferiority margin of 7.0%.

*Note: The primary safety endpoint will be evaluated utilizing only the IDE Study Arm.*

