Success/Failure Criteria	
The study success criterion is to simultaneously demonstrate that the malalignment rate is less than or equal to 0.16 (effectiveness endpoint) and that the composite safety event rate is less than 0.136 (safety endpoint) based on one-sided exact binomial tests with type 1 error rate equal to 0.05. A p-value <math>\leq 0.05</math> for both tests will indicate study success.

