### 9. STATISTICAL PLAN

#### 9.1. Determination of Sample Size for Safety Endpoint

##### IDE Study Arm

The primary safety hypothesis for this study is that the probability of experiencing the composite safety endpoint for patients undergoing TCAT-assisted implantation using the TSolution One System for TKA is not clinically significantly elevated relative to the historic control value of 7.6% for manual TKA. Symbolically, the primary safety hypotheses regarding non-inferiority relative to historical control may be represented as follows:

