**$H_0: \pi_i \geq \pi_c + \delta$  (clinically inferior safety)**

**$H_A: \pi_i < \pi_c + \delta$  (not clinically inferior safety)**

In this formulation,  $\pi_i$  and  $\pi_c$  are the true event rates when using the investigational device and manual TKA, respectively. As noted above, based on a literature review,  $\pi_c = 0.076$ . A non-inferiority margin of 0.06 was selected. Therefore, these hypotheses reduce to:

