**$H_0: \pi_{\text{composite}} \geq 0.076 + 0.06 = 0.136$**

**$H_A: \pi_{\text{composite}} < 0.076 + 0.06 = 0.136$**

A one-sided Fisher's exact test will be used to test the primary safety hypothesis that the composite safety event rate is larger than historical control (0.076) plus the non-inferiority margin of  $\delta=0.06$ . That is, the null hypothesis is that the investigational device event rate is 0.136 or larger and the alternative hypothesis is that this event is less than 0.136. Based on the Sponsor's expectation that the technology is associated with improved outcomes, it was assumed for the purpose of sample size determination that that composite safety event rate for patients undergoing primary TKA with femoral and tibial preparation by the TSolution One™ Surgical System is 20% smaller than control, or equal to 0.0608. A one-sided type 1 error of  $\alpha=0.05$  was

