**The total sample size to be enrolled is equal to 115 (103 plus 10% for possible loss-to-follow-up).**

It can be noted that with N=103, the number (%) of patients experiencing the primary composite safety event must be no larger than 8 (7.8%) in order to achieve the primary study success criterion. With 8 of 103 patients experiencing the event, the upper bound of the one-sided 95% exact binomial confidence interval will be 0.1358 which is less than 0.136, thereby permitting rejection of the inferiority hypothesis and a conclusion of no clinically significant increase in the incidence of the composite safety endpoint.

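### The 7.6% safety reference is a sum of component rates used as a patient-level rate; it is an upper bound, and at N=103 the stated pass of 8 events depends on it

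*Combined protocol and SAP*

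**What the plan says.** Table 1 in Section 5 lists seven complications of primary TKA, each with its own literature rate. Section 5.2 and the Study Summary (Outcome Measurements) add them: "The sum of these relatively rare complications is equal to 7.6"%. Section 5.2 then states the comparison on a per-patient scale: "The percentage of patients with TCAT-assisted implantation experiencing the composite safety event will be compared to 7.6% plus a non-inferiority margin of 7.0"%.

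Section 9.1 carries the sum forward as the true manual-TKA event rate. It frames non-inferiority "relative to the historic control value of 7.6% for manual TKA" and sets the control rate at 0.076. It adds the margin ("A non-inferiority margin of 0.06 was selected") to reach a null of 0.136. The Study Summary uses the same 0.136 in its success criterion, "based on one-sided exact binomial tests with type 1 error rate equal to 0.05", and repeats the hypotheses.

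For power, the device rate "is 20% smaller than control, or equal to 0.0608". Section 9.1 reports 82.5% power at N=103. It says that "the number (%) of patients experiencing the primary composite safety event must be no larger than 8 (7.8"%), because the one-sided 95% exact upper bound for 8/103 is 0.1358, below 0.136.

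I found no statement that the seven complications are mutually exclusive, and no adjustment for a patient who has more than one.

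**The concern.** The two sides of the comparison are on different scales. The trial side is the proportion of patients with at least one component. The reference side is the sum of the component proportions. The two agree only if no patient ever has two components. Otherwise the sum is the larger, so the error can only raise the threshold the device has to beat. Table 1 does not rule out overlap: periprosthetic fracture includes the patella and extensor mechanism disruption is a separate row, and nothing stops one patient having both.

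For rare events the gap is small. It matters because the design point has almost no slack. The stated bound of 0.1358 clears 0.136 by 0.0002, so a correction of a few tenths of a percentage point is enough to change the stated pass mark and power at N=103.

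**Working it through.** **Inputs.** Component rates (Table 1): 2.7%, 2.1%, 1.3%, 0.68%, 0.5%, 0.2%, 0.15%. Margin 0.06, one-sided alpha 0.05, N=103 and device rate 0.0608 = 0.8 × 0.076 (Section 9.1). Exact binomial test (Study Summary).

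**Rule.** The pass mark is the largest c with P(X ≤ c | N, p0) ≤ 0.05. Power is P(X ≤ c | N, device rate). The upper bound is the one-sided 95% Clopper-Pearson limit.

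**Step 1: the plan's own figures.** The sum is 2.7 + 2.1 + 1.3 + 0.68 + 0.5 + 0.2 + 0.15 = 7.63%, given as 7.6%. With p0 = 0.136 and N=103, P(X ≤ 8) = 0.0494, so the pass mark is 8. The upper bound for 8/103 is 0.13578 and power is 82.5%. All of these agree with Section 9.1, and its list of powers for N=102 to 122 reproduces to within 0.1 point.

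**Step 2: patient-level rate if the components are independent (an assumption).** 1 − (0.973 × 0.979 × 0.987 × 0.9932 × 0.995 × 0.998 × 0.9985) = 1 − 0.92587 = 7.41%. The overlap is 7.63 − 7.41 = 0.22 percentage points.

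**Step 3: the test at N=103.** p0 = 0.0741 + 0.06 = 0.1341.

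- 8/103: P(X ≤ 8) = 0.0550, and the upper bound 0.1358 exceeds 0.1341, so it fails.
- 7/103: P(X ≤ 7) = 0.0265, upper bound 0.1239, so it passes. The pass mark is 7.
- Power at the plan's own rule, 20% below control (0.8 × 7.41% = 5.93%): 73.3%.
- Power if the printed device rate of 0.0608 is kept: 71.1%.
- The smallest N with power of at least 80% moves from 103 to 105.

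**Step 4: tipping point.** 8/103 passes only if the reference is at least 0.1358 − 0.06 = 7.58%. Overlap of more than about 7.63 − 7.58 = 0.05 points therefore makes it fail.

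**Step 5: range of references, margin 0.06, N=103.**

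| Reference | Threshold | p for 8/103 | Pass mark |
|---|---|---|---|
| 7.63% (no patient has two components) | 13.63% | 0.0485 | 8 |
| 7.60% (as printed) | 13.60% | 0.0494 | 8 |
| 7.50% | 13.50% | 0.0523 | 7 |
| 7.41% (independence) | 13.41% | 0.0550 | 7 |
| 7.0% | 13.0% | 0.0692 | 7 |
| 6.0% | 12.0% | 0.117 | 6 |
| 2.7% (all events nested; the extreme) | 8.7% | 0.455 | 4 |

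**Step 6: other sample sizes (threshold 13.6% against 13.41%).**

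| N | Pass mark at 13.6% | Pass mark at 13.41% |
|---|---|---|
| 103, 104 | 8 | 7 |
| 105 to 112 | 8 | 8 |
| 113 | 9 | 8 |
| 114, 115 | 9 | 9 |

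At N=115, power at 0.0608 is 83.8% under both thresholds.

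**Step 7: the other margin.** Section 5.2 says "plus a non-inferiority margin of 7.0"%. With 7.41% + 7.0% = 14.41%, p for 8/103 is 0.030 and it passes.

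**The case against.** The strongest reply is that nothing is miscalculated. The addition is right, it is openly called a sum, the complications are rare, and every stated figure follows from 0.136. That stands: the defect is an unstated no-overlap assumption, not faulty arithmetic.

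Second, 7.41% is not a known patient-level rate. The seven rates come from several different cited sources and no joint rates are given, so independence is itself an assumption. This also stands. A reader might infer that the reference should simply be replaced by 7.4% and the threshold by 13.4%. The documents do not support that as the one correct value: positive association would lower the rate further, and near-exclusive events would leave it close to 7.63%. Only the direction is certain.

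Third, a reader might infer that the trial's pass rule fails in general. It does not. The plan enrols 115 and Section 9.3 uses the ITT set for safety; if all 115 are evaluable, the pass mark is 9 either way. Still, Section 9.1 states its pass mark and headline power at 103, so the affected figures are the ones the plan prints.

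Fourth, a reader might take 71% as the corrected power. That lowers the control rate but keeps a device rate defined from the old one. The plan's 20% rule gives 73.3%.

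Finally, the conflict between the 6% and 7.0% margins is one full point, more than four times the 0.22-point overlap, and under 7.0% the result at 8/103 does not turn. The working here uses 0.06 because the formal success criterion and the power calculation do.

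**Conclusion.** The point holds as a minor one. The reference is an upper bound presented as a rate, and the threshold is lenient by an amount the documents do not let us fix. Under independence and a 0.06 margin the amount is about 0.2 percentage points. That costs one event in the pass mark at N=103, 104 and 113, and about 9 to 11 points of stated power at N=103 (82.5 − 73.3 = 9.2; 82.5 − 71.1 = 11.4). At the other sizes from 103 to 115 it does not move the pass mark. The conclusion at 8/103 is secure only with almost no overlap between components (a reference of about 7.58% or more) or if the larger margin applies.

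**What to change.** First reconcile the 6% margin (Study Summary, Section 9.1) with the 7.0% in Section 5.2, because the effect on 8/103 depends on it. Then make these changes together in the Study Summary (Outcome Measurements, Success/Failure Criteria, Hypotheses) and in Sections 5.2 and 9.1:

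- Label the Table 1 sum as an upper bound on the proportion of patients with any component.
- State the reference as a patient-level rate with its overlap assumption: 7.4% if independence is declared, with a range for positive association.
- Restate the threshold, device rate, pass mark and power from that reference. With the 0.06 margin and independence these are 13.4%, 5.93%, 7 of 103 and 73.3%. If 0.0608 is kept instead, say so and report 71.1%.
- Give the pass mark for each evaluable N from 103 to 115, so that the rule does not hang on one sample size.

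Editing only Sections 5.2 and 9.1 would leave the formal success criterion in the Study Summary at 0.136. No new data or procedures are needed. The cost is an amended primary null threshold, slightly stricter than now, and a lower stated power at N=103.

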#### THINK Surgical, Inc.

Proprietary rights of THINK Surgical, Inc. are involved in the subject matter of this material. It is submitted in confidence for a specific purpose and the recipient by accepting this material agrees that it will not be used other than for the express purpose for which it was delivered.

Disclosure to others without written permission from THINK Surgical, Inc. is forbidden.

assumed. Using industry standard software (nQuery Advisor 7.0, Module POT0x-1), it was determined that statistical power to reject the non-inferiority hypothesis was equal to 82.5% with a sample size of N=103. Because of the discreteness of the exact binomial distribution, the power curve is not monotonic. Power for sample sizes of N=102, 103, 104, 105, 106, 107, 108, 109, 110, 111, 112, 113, 114, 115, 116, 117, 118, 119, 120, 121 and 122 are 71.9%, 82.5%, 81.8%, 81.1%, 80.3%, 79.6%, 78.9%, 78.1%, 77.3%, 76.6%, 75.8%, 84.9%, 84.3%, 83.7%, 83.1%, 82.5%, 81.8%, 81.1%, 80.5%, 79.8%, and 87.6%. The smallest sample size with power  $\geq 80\%$  is 103. For sample sizes of N=103 and above, power never falls below 75.8%. The minimum sample size for which power remains at least equal to 80% at that value for all larger values is N=113.

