#### IDE Study Arm

The primary effectiveness endpoint, the safety endpoint and all secondary endpoints including bleeding and the individual components of the composite safety endpoint, will each be summarized by counts, percentages, and the upper bounds of one-sided 95% exact binomial confidence intervals (CI).

Patient function and health-related quality-of-life will be similarly addressed by summarizing baseline, 6-week, 3-month, 6-month, and 12-month (if available) reported outcomes and change at each time point in the Knee Society Scores and SF-12 Health Survey Physical and Mental Health Composite Scores (PCS & MCS), using descriptive statistics including mean, standard deviation, median, minimum, and maximum. The ITT analysis set will be used in all safety analysis. Specific analyses may be repeated in a Per Protocol analysis set that requires completion of the index procedure and no clinically significant protocol violations.

Intraoperative and immediate postoperative complication rates will be similarly summarized using descriptive statistics.

In addition to the above analyses, key safety and effectiveness results will be stratified by certain baseline characteristics (investigational site, age, gender, and median value of Knee Society Score) to confirm that the safety and efficacy of the TSolution One™ Surgical System is consistent among different subgroups.

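### Section 5.2 sets the primary safety margin at 7.0 points (threshold 14.6%), while the success criterion, hypotheses, power and decision rule use 6 points (13.6%)

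*Combined protocol and SAP*

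**What the plan says.** Section 5.2, which defines the primary safety endpoint, says the percentage of patients "experiencing the composite safety event will be compared to 7.6% plus a non-inferiority margin of 7.0" per cent. That puts the threshold at 7.6% + 7.0% = 14.6%.

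The other places that state a margin or threshold use the smaller value:

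- Study Summary, Success/Failure Criteria: success requires that the "composite safety event rate is less than 0.136 (safety endpoint") on a one-sided exact binomial test at 0.05.
- Study Summary, Hypotheses, and Section 9.1: "A non-inferiority margin of 0.06 was selected", and the boundary is written out as 0.076 + 0.06 = 0.136.
- Section 9.1, in prose: "the null hypothesis is that the investigational device event rate is 0.136 or larger".
- Section 9.1, decision rule: with N=103 the number of patients with an event "must be no larger than 8 (7.8%) in order to achieve the primary study success criterion", supported by an upper bound of 0.1358 that is compared with 0.136.

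Two lesser wording points concern the same test. The Study Summary's endpoint description says the percentage "experiencing the composite safety event will be compared to 7.6" per cent and gives no margin. Section 9.1 names a one-sided Fisher's exact test, whereas the Study Summary specifies an exact test for a single proportion.

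**The concern.** The margin fixes the pass/fail limit of one of the two primary endpoints, and both must succeed for the study to succeed. The plan gives two values for it, and the outlying one stands in the section that defines the endpoint. The revision history records no change of margin, and nothing says which section governs.

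If the trial ends on the one event count where the two thresholds disagree, it fails the success criterion but meets the margin in Section 5.2. In a single-arm study compared with a literature constant, that leaves a choice of threshold open after the results are known.

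**Working it through.** **Inputs.** Control rate 0.076, margin 0.06, assumed device rate 0.0608, one-sided alpha 0.05, N=103 evaluable and 115 enrolled (Section 9.1). Alternative margin 0.07 (Section 5.2). Exact binomial test for a single proportion (Study Summary).

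**Formulas.** The limit c is the largest count with P(X ≤ c | N, p0) ≤ 0.05, where p0 is the threshold. Power is P(X ≤ c | N, 0.0608). The upper bound is the one-sided 95% Clopper-Pearson limit.

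**1. Reproduce the plan's own figures, p0 = 0.136, N = 103.**
- P(X ≤ 8) = 0.0494 and P(X ≤ 9) = 0.0924, so c = 8, as stated.
- The upper bound at 8/103 is 0.1358, as stated.
- Power is 82.5%, as stated.
- The smallest N with at least 80% power is 103, as stated.

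**2. Which threshold produced the printed power list?** Section 9.1 prints power for every N from 102 to 122, with the remark "Because of the discreteness of the exact binomial distribution, the power curve is not monotonic". A selection:

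| N | Stated | p0 = 0.136 | p0 = 0.146 |
|---|---|---|---|
| 102 | 71.9% | 71.9% | 83.2% |
| 103 | 82.5% | 82.5% | 82.5% |
| 104 | 81.8% | 81.8% | 81.8% |
| 105 | 81.1% | 81.1% | 89.4% |
| 112 | 75.8% | 75.8% | 85.6% |
| 113 | 84.9% | 85.0% | 91.7% |
| 115 | 83.7% | 83.8% | 90.9% |
| 121 | 79.8% | 79.8% | 93.5% |

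Over all 21 values the largest difference is 0.1 point under 0.136. Under 0.146 only N=103 and 104 match, and the other 19 differ by 5.6 to 13.7 points. Under 0.146 the smallest N with at least 80% power would be 87, not 103. The design was therefore calculated at 13.6%.

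**3. Does the choice change the limit?**

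| N | Events allowed, 13.6% | Events allowed, 14.6% |
|---|---|---|
| 102 | 7 | 8 |
| 103–104 | 8 | 8 |
| 105–112 | 8 | 9 |
| 113–115 | 9 | 10 |

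At N=103, nine events also fail against 14.6% (p=0.054), so the two margins agree there.

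**4. A result on which they disagree.** For 10/115 the upper bound is 14.30%. Against 13.6%, p = 0.075 (fail). Against 14.6%, p = 0.042 (pass).

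**5. How likely is that count?** P(X = 10 | 115, 0.0608) = 7.1%. P(X = 10 | 115, 0.076) = 11.9%.

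**6. Error rate at the plan's stated null.** If the true rate is 13.6%, the limits derived from 14.6% pass with these probabilities:

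| N | Pass probability |
|---|---|
| 105 | 8.10% |
| 112 | 5.01% |
| 113 | 8.55% |
| 115 | 7.52% |

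Throughout N=105 to 115 the value is above 5%, with its low at N=112 and its high at N=113.

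**The case against.** The strongest reply is that the rule is not really open. The only passage headed as a success criterion says 0.136, the hypotheses repeat it twice, and Section 9.1 works it through to an event count. On that reading Section 5.2 is a single descriptive sentence with a slip, and 10/115 plainly fails. This is probably how most readers would resolve it. But Section 5.2 is the endpoint definition, and the plan has no rule of precedence.

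The effect is also narrow, and that stands. At the N on which the study is powered nothing changes, and elsewhere only one event count is in dispute. The N=115 example assumes no attrition. Section 9.3 says "The ITT analysis set will be used in all safety analysis", which favours an N near full enrolment, but the ITT set is not defined. Section 6.5 treats patients who withdraw before treatment as screen failures, and Section 8.3 bars data from those who withdraw consent. The analysed N is therefore uncertain. Even so, the limits differ at every N from 105 to 115.

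The error-rate figures in step 6 take 13.6% as the null. Against its own null of 14.6% the larger limit keeps alpha at 2.7% to 4.9% over N=105 to 115. Step 6 thus restates the same discrepancy and is not a separate harm.

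Finally, the power list shows which margin was used in the calculations, not which is clinically justified. The documents give no clinical justification for either.

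**Conclusion.** The contradiction is real and stands in current text. The 7.0% in Section 5.2 is the outlier: the success criterion, both statements of the hypotheses, the power list and the 8-of-103 rule all rest on 13.6%. The consequence is a difference of one event in the limit of a primary endpoint at every N from 105 to 115, and none at 103 or 104. At N=115 the chance of ending on the disputed count is 7.1% at the planned rate and 11.9% at the control rate. These figures assume the one-sample exact binomial test at one-sided 0.05, which reproduces every safety figure the plan states. This needs correcting before analysis, because it concerns a primary decision threshold. The missing margin in the Study Summary and the Fisher wording are minor and do not add to its weight.

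**What to change.** In Section 5.2, replace the margin of 7.0% with 6.0% and state the resulting threshold of 13.6%, so that the endpoint definition matches the success criterion and the power calculation.

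Make two accompanying wording corrections:

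- In the Study Summary's description of the primary safety endpoint, add that the comparison is with 7.6% plus a non-inferiority margin of 6.0%.
- In Section 9.1, replace Fisher's exact test with the one-sided exact binomial test for a single proportion. The comparator is a fixed constant, so there is no second sample for a Fisher test.

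The cost is wording only: the 103 evaluable and 115 enrolled patients, the 82.5% power and the success criterion are unchanged. For the sponsor, the threshold in Section 5.2 becomes one point stricter. At N=115 and a true rate of 6.08%, power is 83.8% under 13.6% against 90.9% under 14.6%. The plan never claimed the higher figure; Section 9.1 prints 83.7% for that N.
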